### Immune-related Endpoints

The irRC incorporates several elements reflecting the complex tumor dynamics of ipilimumab treatment. Under these criteria, a measure of tumor volume is used that incorporates the contribution of new measurable lesions. Each net percentage change in tumor burden per assessment using irRC accounts for the size and growth kinetics of both old and new lesions as they appear. New lesions alone do not qualify as irPD.

In this study, irRC will be used to assess subject response to study treatment per investigator assessment. The endpoint irPFS will be determined based on investigator assessment. In order to adequately address this objective, investigators will obtain confirmatory scans beyond RECIST PD and follow the instructions in this section for the determination of immune-related response.

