### **Definition of Tumor Response Using irRC**

#### **Calculation of Immune-related Sum of Products of Diameters (irSPD)**

The irSPD incorporates measurable new lesions that may have developed on-study, providing an assessment that includes both index and new lesions. The tumor assessment performed during Screening will serve as the baseline for determination of tumor response using irRC.

irSPD at Baseline: The sum of the product of the diameters for all index lesions identified prior to randomization. At baseline, irSPD and SPD are the same.

irSPD at TA: For every post-randomization TA collected, per protocol Section 5.1 or as clinically indicated including post mWHO PD TA, the irSPD at TA will be calculated using tumor imaging scans. Both index lesions and any measurable new lesions that have developed on study will be included.

irSPD Nadir: For tumors that are assessed more than one time after baseline, the lowest value of the irSPD (irSPD Baseline or irSPD at TA) is used to classify subsequent TAs for each subject. Because ipilimumab treatment may result in complex tumor dynamics in which index lesions may shrink while new lesions appear, the irSPD nadir may be different from the SPD nadir, and may occur either before or after the SPD nadir.

At baseline, the irSPD is measured and recorded.

At each subsequent assessment timepoint, a separate assessment of timepoint overall response will be obtained for that timepoint. The sum of products of perpendicular diameters calculated and recorded at each post-baseline timepoint for immune-related response purposes (irSPD) include measurements of index lesions and also include measurable new lesions which are not too small to measure at this timepoint. A value of 25 mm^2 (5 mm x 5 mm) is imputed for each index and previously measurable new lesion which is present but too small to measure.

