### Timepoint Overall Response Using irRC

- The overall assessment of immune-related response reported at each timepoint will be based on the following criteria:
- Immune-related CR (irCR): Complete disappearance of all tumor lesions (index and non-index together with no new measurable/unmeasurable lesions).
- Immune-related PR (irPR): A decrease, relative to baseline of the irSPD (as defined above) of 50% or greater is considered an irPR.
- Immune-related SD (irSD): irSD is defined as an evaluable response that fails to meet criteria for immune-related CR or immune-related PR, in the absence of irPD.
- Immune-related Progressive Disease (irPD): At least a 25% increase in the irSPD (based on irSPD of all index lesions and any measurable new lesions, as defined above) over the nadir irSPD, or the occurrence of any new measurable lesions if the SPD nadir is “0” (including when no measurable lesions are present at baseline).
- Immune-related Unknown Response (irUN): Tumor assessments which cannot be evaluated (e.g., due to image quality, inability to assess all relevant lesions, etc.) will be reported as irUN.

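### The new-lesion limb of irPD is triggered by an SPD nadir of zero rather than an irSPD nadir of zero, so a patient with cleared index lesions and falling total burden can meet irPR and irPD on one scan

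*Combined protocol and SAP*

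**What the plan says.** All the relevant text is in protocol Section 9.1.

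- *Timepoint Overall Response Using irRC* gives irPD two limbs. The first is "At least a 25% increase in the irSPD (based on irSPD of all index lesions and any measurable new lesions, as defined above"), measured over the nadir irSPD. The second is "the occurrence of any new measurable lesions if the SPD nadir is" zero, with a bracket extending it to patients who have no measurable lesion at baseline.
- The same list sets irPR by burden alone: "A decrease, relative to baseline of the irSPD (as defined above) of 50% or greater is considered an irPR". Of the response categories only irSD mentions irPD; it applies when a response "fails to meet criteria for immune-related CR or immune-related PR, in the absence of irPD".
- *Calculation of Immune-related Sum of Products of Diameters (irSPD)* says of irSPD after randomization: "Both index lesions and any measurable new lesions that have developed on study will be included". It also says "At baseline, irSPD and SPD are the same", and warns that "the irSPD nadir may be different from the SPD nadir, and may occur either before or after the SPD nadir".
- *Immune-related Endpoints* states the principle: "New lesions alone do not qualify as irPD".

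Section 12.3, *Efficacy Analyses*, makes PFS, overall response rate, duration of response and duration of stable disease under irRC additional secondary endpoints. It defines progression for the primary PFS by RECIST v1.1.

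**The concern.** One definition uses two different nadirs. The 25% limb looks at total burden, index plus measurable new lesions. The new-lesion limb looks at SPD, which on the most natural reading is the index lesions only. The two part company in the situation the protocol gives as its reason for distinguishing them: index lesions shrink while new ones appear. When the index lesions have gone but a measurable new lesion remains, the SPD nadir is zero and the irSPD nadir is not. The new-lesion limb can then declare progression whatever total burden is doing.

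The same scan can satisfy irPR, and nothing says which category prevails. irRC is assessed by the investigator in an open-label trial, so an unresolved choice between response and progression would be made with the arm known. What is at stake is the date of irPFS events and the irRC durations in patients whose tumour burden has fallen most.

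**Working it through.** There is no stated figure to reproduce. The check applies the written rules to lesion histories. Lesion sizes are assumptions; the rules are the protocol's.

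**Inputs from Section 9.1**
- irSPD = index lesions + measurable new lesions; SPD = index lesions (inferred, see the objection).
- irPR: (baseline irSPD − current irSPD) / baseline irSPD ≥ 50%.
- irPD, limb 1: (current irSPD − nadir irSPD) / nadir irSPD ≥ 25%.
- irPD, limb 2: SPD nadir = 0 and a new measurable lesion occurs.

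**Main history**

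| | Index | New A | New B | SPD | irSPD |
|---|---|---|---|---|---|
| Baseline | 2000 | – | – | 2000 | 2000 |
| Scan 1 | 0 | 150 | – | 0 | 150 |
| Scan 2 | 0 | 36 | 100 | 0 | 136 |

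(all in mm²)

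Scan 1: (2000 − 150) / 2000 = 92.5% fall, so irPR.

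Scan 2:
- irPR: (2000 − 136) / 2000 = 93.2% fall, met.
- irPD limb 1: (136 − 150) / 150 = −9.3%, not met.
- irPD limb 2: SPD nadir 0 and new lesion B, met.

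Scan 2 is therefore both irPR and irPD.

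**Sensitivity to wording.** Two things are open: whether the SPD nadir uses prior scans only or includes the current scan, and whether occurrence means first appearance or mere presence. Scan 2 is both irPR and irPD under all four combinations, because SPD was already zero at scan 1 and B is new at scan 2. If the nadir includes the current scan, scan 1 is already both.

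**Control.** Leave an index remnant of 25 mm², the value the protocol imputes for a lesion present but too small to measure, with total burden 150 and then 145 mm². At scan 2 the change from nadir is (145 − 150) / 150 = −3.3% and the fall from baseline is (2000 − 145) / 2000 = 92.8%. The SPD nadir is 25, so limb 2 does not apply and the result is irPR only. Full index clearance alone turns the similar burden into irPD.

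**With limb 2 triggered by irSPD nadir = 0.** In the main history the irSPD nadir is 150 at scan 2, so limb 2 does not apply and both scans are irPR only. A genuine recurrence after irSPD has reached zero is still irPD. Patients with no measurable baseline lesion are still covered, because SPD and irSPD are equal at baseline.

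**What that change alone does not cure**
- Baseline 2000, irSPD nadir 100, now 130: limb 1 gives (130 − 100) / 100 = +30%, irPD; the fall from baseline is (2000 − 130) / 2000 = 93.5%, irPR.
- Baseline 2000, irSPD nadir 0, then a new 100 mm² lesion: limb 2 gives irPD; the fall from baseline is (2000 − 100) / 2000 = 95%, irPR.

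Both need a precedence rule.

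**The case against.** The strongest reply is that this is a matter of terms. SPD after baseline is never defined, and *New Lesion Measurement* in Section 9.1 speaks of an SPD that includes new lesions. A zero-nadir clause is also what one needs where a percentage rise over the irSPD nadir is undefined, so an analyst might read SPD nadir as shorthand for irSPD nadir. It stands that index-only SPD is an inference. But that subsection has to add the inclusion of new lesions explicitly, and the irSPD subsection says the two nadirs can differ. The literal reading is the better supported one, and on either reading the text needs correcting.

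It also stands that part of the overlap comes from the missing precedence rule rather than from the trigger, as the last two histories show. And any zero-nadir clause is an exception to the principle that new lesions alone are not irPD; the fix narrows that exception without removing it.

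Three stronger readings are tempting and are not supported.

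- A reader might infer that an existing, unchanged new lesion produces irPD on the scan where the index lesions first clear. Take baseline 1500; scan 1 index 600 plus new 120 = 720 mm² (52% fall); scan 2 index 0 plus the same 120 mm² (92% fall). Scan 2 is irPD in only one of the four readings: nadir including the current scan, and occurrence meaning presence. The protocol applies the irSPD nadir to later assessments, and an unchanged lesion is not obviously a new occurrence.
- A reader might infer that the irRC response rate is biased. That is not shown. Section 12.3 counts stable disease or better as response, and with a prior-scan nadir the patient in the main history is already irPR at scan 1.
- A reader might infer that the primary result is at risk, since Section 9.1 sends some suspected progressions to irRC before they count. Section 12.3 nevertheless defines progression for the primary PFS by RECIST v1.1.

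**Conclusion.** The defect is real and limited. As written, once all index lesions have cleared, a further measurable new lesion is irPD even if total burden has fallen, while the same scan can meet irPR. The error runs towards progression and falls on patients with complete index clearance.

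It bears on secondary endpoints, mainly irPFS and the irRC durations of response and of stable disease. Section 12.3 applies no formal testing to secondary endpoints, and the sample size is unaffected. The documents give no frequency for this pattern, so no overall effect can be stated. One such patient in an arm of 50 moves the crude proportion free of irPD by 1/50 = 2 percentage points, and only at a time when that patient would otherwise be free of irPD.

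The conclusion rests on reading SPD as index lesions only. The percentages are illustrative: they follow from the assumed sizes, and any fall of at least 50% from baseline creates the same conflict.

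**What to change.** In Section 9.1, *Timepoint Overall Response Using irRC*:

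1. In the new-lesion limb of irPD, replace SPD nadir with irSPD nadir, keeping the bracket on patients with no measurable lesion at baseline.
2. State that the nadir is the lowest irSPD before the scan being classified.
3. Make irPR conditional on the absence of irPD under either limb: a rise of at least 25% over the irSPD nadir, or a new measurable lesion after an irSPD nadir of zero. A precedence rule for the 25% limb alone would leave the recurrence-after-zero case unresolved.

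The cost is a short wording change in the irRC definition and the matching change in the response program. No new data are needed: irSPD is already to be calculated at every assessment, and the measurements of new lesions are already recorded in the CRF.

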## 10 REGULATORY AND REPORTING REQUIREMENTS

### 10.1 *Subject Data*

Subject data accrued on this study will be reported in accordance with 21CFR 312.32.

### 10.2 *CTCAE*

This study will utilize the CTCAE Version 4.03 for Adverse Event (AE) Reporting. The CTCAE v4.03 can be downloaded from the CTEP home page (<http://ctep.info.nih.gov>).

### 10.3 *Notifications*

The P.I. will notify the IRB, OBA, and NewLink Genetics (Study Sponsor) who in turn will notify the FDA and other regulatory agencies of all serious adverse events as required by law or regulation. All participating investigators will be notified of IND Safety Reports by *Investigator Alerts* sent through email.

### 10.4 *Definitions for Reporting Purposes*

In this protocol the study drug dorgenmeltucel-L is being combined with one of three different immune checkpoint immunotherapies, drugs with an established safety profile. Adverse events and serious adverse events observed during the course of this trial and previously reported as related to ipilimumab, nivolumab, or pembrolizumab will be attributed to such. Adverse events previously seen with dorgenmeltucel-L or other HyperAcute therapies will be attributed to dorgenmeltucel-L. Novel serious adverse events not previously seen with any study agent will initially be considered regimen associated and will require an evaluation by the PI and the sponsor

to determine attribution. This will be done via teleconference within three business days of the report.

An **adverse event** (AE) is any symptom, sign, illness or experience that develops or worsens in severity during the course of the study. Intercurrent illnesses or injuries should be regarded as adverse events. Abnormal results of diagnostic procedures are considered to be adverse events if the abnormality:

- results in study withdrawal
- is associated with a serious adverse event
- is associated with clinical signs or symptoms
- leads to additional treatment or to further diagnostic tests
- is considered by the investigator to be of clinical significance

**Related** to the use of the drug: There is a reasonable possibility (more likely than not) that the experience may have been caused by the investigational drug.

A **serious adverse event** is any AE that is:

- fatal
- life-threatening
- requires or prolongs hospital stay
- results in persistent or significant disability or incapacity
- a congenital anomaly or birth defect
- an important medical event

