**Specific Risk/Adverse Events**

Nivolumab can cause severe and fatal immune mediated adverse effects. Many organs systems can be involved. The most common severe adverse events include pneumonitis, colitis, hepatitis, nephritis, and thyroid disease (either hypothyroidism or hyperthyroidism). Additional immune mediated reactions observed include adrenal insufficiency, pancreatitis, neuropathies, hypophysitis, and Guillain-Barre syndrome.

Management of these conditions includes withholding of nivolumab, administration of high-dose corticosteroids, and if appropriate, initiation of hormone replacement therapy.

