**SAE reporting timelines are defined as:**

- “24 Hour; 5 Calendar Days” – The SAE must initially be reported within 24 hours of learning of the SAE, followed by a complete SAE report within 5 calendar days of the initial 24 hour report.

Serious adverse events that occur more than 30 days after the last administration of investigational agent/intervention and have an attribution of possible, probable, or definite to dorgemeltucel-L require reporting on the same timelines as noted above.

Deaths clearly due to progressive disease should **NOT** be reported expeditiously but rather should be reported via routine reporting

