### ***11.3 Evaluation of Benefits and Risks***

The benefits of this immunization approach are theoretical and it is hoped that the induction of an acute rejection response to the  $\alpha(1,3)$ galactosylated residues on the allogenic melanoma cancer cells used to immunize the patient will lead to cross-recognition of weak native tumor antigens on the patient's melanoma cells that may be shared with the genetically engineered immunotherapy cells. By generating an antibody and cellular immune response against the patient's tumor, it is hoped that the patient may benefit by a tumor response.

Given the safety demonstrated with transfer of murine retroviral vector producer cells in several studies that naturally express the  $\alpha(1,3)$ GT enzyme and have 1,3- $\alpha$ -galactosylated residues, and the poor prognosis of this patient population, it is believed that the possible benefits from tumor response and improved survival probability far outweigh the risk to the patient. The information obtained in this study may be extremely valuable in the treatment of melanoma and other malignancies in the future. The patients to be entered in this protocol have refractory or recurrent melanoma and limited life expectancies. The chance of this experimental treatment to provide clinical benefit is unknown. All possible benefits and known risks will be carefully explained to all patients and an Informed Consent Document will be signed by the patient prior to entrance into the protocol.

There are no anticipated serious adverse side effects to the immunization technique employed in this study. Theoretical risks may include the induction of unanticipated autoimmune disease and/or liver, kidney, lung, heart and CNS damage and/or coagulopathy and bleeding as a result of excessive activation of the complement (C') system. Expected risks and discomforts to the patients are minimal and will be those of needle sticks and phlebotomy. An acceptable adverse event profile was developed in the Phase I part of the trial. Patients will be observed for one hour after each immunization for allergic/hypersensitivity reactions. Patients will be treated as deemed medically appropriate for any immediate or delayed adverse event related to the immunization.

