**Safety Analyses**

Adverse events will be summarized by MedDRA system organ class and preferred term. Separate tabulations will be produced for all treatment-emergent adverse events, treatment-related adverse events (those considered by the Investigator as at least possibly drug related), serious adverse events, discontinuations due to adverse events, and adverse events of at least Grade 3 severity. By-patient listings will be provided for deaths, serious adverse events, and events leading to discontinuation of treatment.

Descriptive statistics will be provided for clinical laboratory data and vital signs data, presented as both actual values and changes from baseline relative to each on-study evaluation and to the last evaluation on study.

In addition, shift tables of laboratory data from baseline to worst value on treatment will be presented based on CTCAE v 4.03 grading.

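### Section 10.4 assigns known checkpoint-inhibitor events by precedent, gives no route for potentiation by the vaccine, and contradicts the plan's judgement-based relatedness

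*Combined protocol and SAP*

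**What the plan says.** Section 10.4 contains three attribution sentences and a definition.

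- Events known for a checkpoint inhibitor: those "previously reported as related to ipilimumab, nivolumab, or pembrolizumab will be attributed to such".
- Events known for the vaccine: "Adverse events previously seen with dorgenmeltucel-L or other HyperAcute therapies will be attributed to dorgenmeltucel-L".
- Everything else that is serious: "Novel serious adverse events not previously seen with any study agent will initially be considered regimen associated", followed by a teleconference between investigator and sponsor to decide attribution.
- The definition of Related: "There is a reasonable possibility (more likely than not) that the experience may have been caused by the investigational drug".

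Two later sections use relatedness. Under the SAE timelines in 10.6, serious events more than 30 days after the last dose that "have an attribution of possible, probable, or definite to dorgemeltucel-L require reporting on the same timelines" as earlier ones. In 12.3 (Safety Analyses), the treatment-related table holds events that are "those considered by the Investigator as at least possibly drug related".

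Section 11.3 lists among the theoretical risks of immunization the "induction of unanticipated autoimmune disease and/or liver, kidney, lung, heart and CNS damage". Section 5.3 says of nivolumab: "The most common severe adverse events include pneumonitis, colitis, hepatitis, nephritis, and thyroid disease". Sections 5.2 and 5.4 give similar lists for ipilimumab and pembrolizumab.

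**The concern.** Safety is a primary objective, and section 1.1.1 frames it as a comparison of checkpoint inhibition with and without the vaccine. The rationale in 2.6 is synergy between the two. A foreseeable hazard is therefore more, worse or earlier immune-mediated toxicity of kinds already known for checkpoint inhibitors, rather than a new kind of event. The liver, kidney and lung risks that 11.3 names for the vaccine overlap with the hepatitis, nephritis and pneumonitis listed for nivolumab.

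A rule that looks only at whether an event has been reported before cannot register that hazard. Hepatitis in Arm 1 goes to the checkpoint inhibitor because hepatitis is on its list, whatever the timing, severity or clinical picture. The review that might identify a joint effect is reserved for novel serious events. At stake are the credibility of the related-event tables as evidence on the vaccine and the handling of some late serious events.

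**Working it through.** The point rests on no sample size, alpha or power figure, so there is nothing of the plan's to reproduce. The check sets the sections side by side.

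**1. What decides causality in each place**

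| Place | Basis | Agent judged |
|---|---|---|
| 10.4, attribution sentences | Past reports of the event type | Whichever agent has the precedent |
| 10.4, Related | Causal judgement, more likely than not | Investigational drug |
| 10.6, serious events after 30 days | Possible, probable or definite | Dorgenmeltucel-L |
| 10.6, adverse events after 30 days | Related or not | Study drug or combination |
| 12.3, treatment-related table | Investigator judgement, at least possible | Drug, not specified |

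One row uses precedent and the others require a judgement. The judgement rows also differ in threshold, since possible is a lower bar than more likely than not. One event in Arm 1 can therefore receive different answers depending on which section the site follows.

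**2. Trace a known event.** Take hepatitis in Arm 1, assumed more severe than usual.
- Checkpoint sentence: it applies, and the event is attributed to the checkpoint inhibitor.
- Vaccine sentence: it applies only if hepatitis has been seen with a HyperAcute product. The events that 5.1 names as most frequent are injection site reactions, fatigue and nausea. The documents report no hepatitis, colitis or pneumonitis with the vaccine. The Investigator's Brochure is not available here.
- Novel-event review: it does not apply, because the event type is known.

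None of the three sentences leads to vaccine or combination attribution.

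**3. Trace an event on both lists.** Section 2.3 reports vitiligo in 4 of 25 patients given the vaccine with pegylated interferon. If it is also known for a checkpoint inhibitor, which the documents do not say, both precedent sentences apply and no priority is given.

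**4. Find where attribution changes an output**
- Events on study and to 30 days after the last dose: recorded whatever the attribution (10.6, case report form). Unaffected.
- Serious events: sent to the sponsor within 24 hours irrespective of causality (10.6). Unaffected within 30 days.
- Tables of all treatment-emergent events, serious events and Grade 3 or higher events (12.3): unaffected.
- Treatment-related table (12.3): affected. If drug means any study treatment, the event stays in the table but is not linked to the vaccine. If drug means the vaccine, it drops out.
- Serious events after 30 days (10.6): affected. One assigned only to the checkpoint inhibitor does not meet the vaccine-attribution condition.

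**5. How much the all-causality comparison can carry.** The documents give no control rates, so these are assumed. With n = 50 per arm, p̄ = (p1 + p2)/2 and q = 1 − p:

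power = Φ{[√n·|p2 − p1| − z·√(2p̄q̄)] / √(p1q1 + p2q2)}

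For 10% against 20% at two-sided 0.05: [7.071 × 0.10 − 1.960 × √0.255] / √0.25 = (0.707 − 0.990)/0.5 = −0.57, so power is 29%.

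| Assumed rates | Alpha 0.05 | Alpha 0.20 |
|---|---|---|
| 10% vs 20% | 29% | 55% |
| 15% vs 30% | 43% | 70% |
| 20% vs 40% | 59% | 82% |
| 30% vs 60% | 87% | 97% |

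For a 1.5-fold increase from control rates of 10% to 30%, power at 0.05 is 11% to 34%. The comparison can show large potentiation of common events but is weak for rarer ones. That limit comes from 100 patients, not from 10.4. It is the reason why sound case-level causality is worth having.

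**The case against.** The strongest reply is that the randomised comparison answers the safety question without attribution. Events are captured regardless of cause to 30 days after the last dose, and vaccination in Arm 1 is scheduled to month 24, so most on-treatment immune events fall in that period. All-cause, serious and Grade 3 or higher tables are already planned. This stands, and it confines the point to the outputs in step 4.

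A reader might infer that vaccine potentiation can never be recorded as vaccine-related. The documents do not support that. Neither precedent sentence claims to be exclusive, and the definition of Related, the late serious-event rule and 12.3 each leave room for an investigator to judge an event related to the vaccine. What the documents show is a contradiction, with no statement of which rule prevails.

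A reader might also infer that 10.4 generally reduces safety capture after 30 days. That goes too far. The case report form rule covers events related to the study drug or the combination, and 12.3 counts checkpoint therapy as study treatment, so on that reading an event assigned to the checkpoint inhibitor is still recorded. The gene-transfer monitoring in 10.6 separately requires reports of autoimmune disorders and unexpected hospitalizations, at least yearly for 15 years, with no causality condition. Only the expedited timeline for late serious events remains exposed.

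**Conclusion.** The concern holds in limited form. Section 10.4 sets attribution by precedent, has no route for potentiation of a known checkpoint-inhibitor event, has no tie-break for events known for both agents, and conflicts with the judgement-based relatedness in 10.4, 10.6 and 12.3.

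The consequence is confined to the treatment-related tables and to expedited reporting of serious events more than 30 days after the last dose. No patient count can be put on it, because the documents give neither immune-event rates nor the number of late events. The conclusion assumes that sites apply 10.4 as written. If they follow 12.3 instead, the practical effect shrinks, but the contradiction remains. The correction should be made, but the defect does not undermine the comparison of arms.

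**What to change.** - **10.4:** Replace the precedent sentences. The investigator assesses each adverse event separately for the vaccine, the checkpoint inhibitor and the combination. State that earlier reports with one agent do not by themselves exclude relatedness to another. Do not substitute a default that known immune events in Arm 1 are possibly related to both, because that would be another blanket rule overriding case judgement.
- **10.4, 10.6 and 12.3:** Adopt one relatedness scale and threshold throughout. Say whether a serious event attributed to the combination falls under the late reporting rule, and which agent or agents the treatment-related table refers to.
- **12.3:** Add a by-arm, all-causality summary of immune-mediated events, using a term list fixed in advance, beside the planned Grade 3 or higher table. State that the potentiation question rests on these two summaries rather than on attributed events.

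The cost is revised wording, causality fields on the adverse event form with matching instructions, and one extra table. Somewhat more events will be listed as vaccine-related and reported. Sample size, visits and treatment do not change.
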